9.3.4 Assessment of Adverse Events

• Responsibilities of Investigator

Adverse events are assessed by the investigator in a standardized manner including, but not limited to seriousness, severity, outcome, and causality. This has to be performed in line with the definitions and provisions given in Appendix 1.

Laboratory values outside the reference range have to be assessed for clinical relevance taking into account the pretreatment values. For reporting of abnormal laboratory values as AEs, refer to Section 9.2.1.4.

If an AE meets the definition of any of the mandatory AE related stopping rules (Section 9.3.1), the investigator must withdraw the subject and report the AE as an IRAE according to Appendix 2.

For all AEs, the causality assessment has to be provided in the eCRF, even if based on preliminary data. Once more information is available, the investigator may change a preliminary causality assessment.

During and after participation of a subject in a clinical study, the investigator/institution has to ensure that adequate medical care is provided to the subject for any ongoing AEs, including clinically significant abnormal laboratory values. The investigator has to inform the subject when medical care is needed for any intercurrent disease of which the investigator becomes aware.

EudraCT No.: 2015-003652-52/

Study No.: 991

IND No.: 17046

Adverse events are reviewed and assessed by the sponsor during ongoing safety monitoring activities throughout the study, as well as medical evaluation and regulatory assessment for reportability of SAEs and IRAEs. For the purpose of regulatory reporting, the causality assessment given by the investigator will not been downgraded by the sponsor. If the sponsor disagrees with the investigator's causality assessment, both the opinion of the investigator and the sponsor will be recorded.

Regulatory assessment of an AE by the sponsor comprises the assessment of expectedness, which is based on Section 7 of the Investigator's Brochure for BT595.

• Follow-up of Adverse Events

Adverse events should be followed up to determine the outcome.

Adverse events that are serious or severe or considered related to the study medication or study procedures must be followed-up by the investigator until the AE is resolved or resolved with sequelae, and until all queries related to the AE have been clarified. If the subject had an AE with fatal outcome, an autopsy report should be provided, if possible.

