If AEs that are serious or severe or considered related to study medication or study procedures are ongoing at the time of the subject's last study visit, or if the subject has clinically relevant laboratory parameter abnormalities at the last study visit, one or more safety follow-up visit should be scheduled for those subjects. The investigator should set the interval to the additional Safety follow-up visit according to his/her medical judgment. Follow-up activities should be continued until the investigator considers it medically justifiable to stop further follow-up.

All other AEs must be followed up by the investigator until the AE is resolved or resolved with sequelae or the end of the period of observation (i.e., last study visit), whichever comes first.

The investigator should respond to any queries raised by the sponsor in relation to AEs, including provision of supporting documentation for SAEs or other IRAEs (e.g., electrocardiogram [ECG] data, laboratory results, hospital summary, autopsy report) within the requested timeline. In case of fatal or life-threatening SAEs, the sponsor may request urgent clarification within 1 calendar day. In general, if for AEs requiring immediate reporting from the investigator to sponsor (IRAEs/SAEs), follow-up information becomes available, this must be reported to the sponsor within 24 hours of becoming aware of this information (i.e., the same timeframe as for initial IRAE/SAE reports). Any supporting documents have to be identified by the subject identification, and personal data (e.g., subject name, address, or phone number) obliterated prior to sending to the sponsor. For details on reporting IRAEs/SAEs, see Appendix 2.

Adverse event data in the eCRF must be updated accordingly when follow-up information is received.

All efforts to collect follow-up information must be documented in the subject's source data.

study as per protocol, should receive all the examinations and investigations scheduled for the last study visit. The investigator should make all efforts to contact subjects lost to follow-up and document the attempts in the subject's source data.

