* "At any dose" does not necessarily imply that the subject is receiving the study drug at the time of the event.

• Diagnosis vs Signs/Symptoms

The investigator should provide a diagnosis rather than individual signs and symptoms, wherever possible and appropriate. However, if there is not enough information to provide a diagnosis, individual signs and symptoms are to be recorded. If a diagnosis is accompanied by unusual symptoms, the diagnosis itself and the unusual symptoms have to be reported separately. For SAEs and other IRAEs, the investigator shall provide any other supporting information that may be required for the assessment of the events, specifically in the free text narrative description of the case. This is of particular importance in situations where a diagnosis cannot (yet) be made. Any subject identifying data on

supporting documents (e.g., name, address, phone number) have to be obliterated prior to sending them to the sponsor.

A complication of an AE constitutes another AE. For example in diarrhea leading to dehydration, diarrhea and dehydration would be captured as separate AEs.

The eCRF provides for a number of items to be completed for each AE. This includes the onset date, end date, intensity/severity, seriousness, action taken with study medication, treatment for the AE, outcome, and causal relationship of the AE with the study medication, other drugs, or study procedures.

• Onset Date, End Date

If an AE started during the study but did not end before the final closing (follow-up) visit, the investigator must make a reasonable effort to establish the outcome and the end date. If this is not possible, e.g., because the AE is still ongoing, or the subject is lost to follow-up, there will be no end date for the AE.

For all AEs that resolve, resolve with sequelae, or have a fatal outcome, an end date must be provided.

If an AE stops and restarts later, all occurrences have to be recorded separately.

If an AE starts as a nonserious AE and becomes serious at a later point in time, the following applies in regard to onset and end dates:

• Intensity/Severity

Refers to the extent to which an AE affects the subject's daily activities. Severity will be categorized according to the following criteria:

	•
Mild	The AE does not interfere with the subject's routine activities.
Moderate	The AE interferes with the subject's daily routine, but usual routine activities can still be carried out.

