# 6.3. MISSING DATA

All available data will be included in the analyses and will be summarized as far as possible. Unless otherwise specified, there will be no substitution of missing data, i.e., missing data will not be replaced; missing data will be handled as 'missing' in the statistical evaluation.

Incomplete/missing start and stop date/time for AEs/antibiotic treatments will be handled as follow:

Start date will be imputed

- Missing start day with the day of first drug administration within that month. If no drug was administered then with '01'.
- Missing start day and month with the 1st of January. If the AE/antibiotic treatment start year = year of the first drug administration then with the date of the first drug administration.
- Missing start year with the date of the first drug administration
- In case an Investigator comment is available, imputation will take this into account:
  - o AE started before the day of a drug administration: missing start day with '01'
  - AE started after the day of a drug administration: missing start day with one day after the day of drug administration
  - AE started at least 72 hours after the day of a drug administration: missing start day with four days after the day of drug administration

Stop date will be imputed

- Missing stop day with last day (28/29/30/31) of the month.
- Missing stop day and month with 31st of December.
- Missing stop year with the date of study termination.

- Incomplete AE stop dates will only be imputed in case of the AE is not ongoing.

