#### 8.2.2. Rate of Any Infections

Infections are identified by the following criteria:

- Any AE leading to the MedDRA SOC "infections and infestation".
- All AEs leading to any other SOC are reviewed by the sponsor for possible relation to an infection (e.g. pyrexia leading to SOC General disorders and administration site conditions). Identified AEs possibly related to this endpoint are queried to the investigator. The investigator transfers his decision to the eCRF (AE term).

The annual rate of infections will be calculated as the mean number of all infections (serious plus nonserious) per subject-year as described in Section 8.1.1. The annual rate per subject will be the total number of infections of the subject divided by the total duration expressed in years of the observation period of the subject. Summaries will be as for a continuous variable and by categorizing the number of any infections per subject according to the following categories:

- 0
- 1
- 2
- 3 to <5
- 5 to <10
- ≥10

The annual rate of days with infections per subject will be the total number of days with infections of the subject divided by the total duration expressed in years of the observation period of the subject.

Frequency tables presenting the number (%) of subjects with infections, the number of days with any infections and the total number of infections will be done.

Tables will also be stratified by season (spring, summer, autumn, winter) using the calendar whereas e.g. spring starts on 01Mar.

In addition, summaries will be done for the subgroup of subjects that did not receive treatment for the full period of time, either by missing an infusion or discontinuing the study.

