#### 8.2.4. Time to Resolution of Infections

Time to resolution of infections (days) will be calculated as infection stop date – infection start date + 1. For the imputation rules of incomplete start/stop dates refer to Section 6.3. The presentation will include the continuous variable and also by categorizing the number of days until the resolution of infection the data according to the following categories:

- 1 to <3
- 3 to <5
- 5 to <8
- 8 to <10
- 10 to <14
- ≥14

Time to resolution will be presented for any infections, serious infections and nonserious infections.

Kaplan-Meier plots will be generated for time to resolution of infection by infusion schedule and overall.

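### Infections still ongoing at the end of observation fall out of the tabulated time-to-resolution summaries, and no rule says how their days are counted

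*SAP*

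**What the plan says.** Infections are recorded as AEs (SAP 8 and 8.2.2), so AE date rules govern them.

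- Protocol Appendix 1 requires a reasonable effort to establish the end date of an AE that is open at the closing visit. If that fails, for example "because the AE is still ongoing, or the subject is lost to follow-up, there will be no end date for the AE".
- Protocol 9.3.4 splits AEs by type. Serious, severe or related AEs "must be followed-up by the investigator until the AE is resolved or resolved with sequelae". If they are open at the last visit, extra safety visits are scheduled: "Follow-up activities should be continued until the investigator considers it medically justifiable to stop further follow-up". All other AEs are followed no later than the last study visit.
- SAP 6.3 leaves missing data unreplaced by default: "missing data will be handled as 'missing' in the statistical evaluation". It gives imputation rules for incomplete AE and antibiotic dates, including "Missing stop year with the date of study termination", and then adds the restriction "Incomplete AE stop dates will only be imputed in case of the AE is not ongoing". The restriction names AEs, not antibiotics.
- SAP 8.2.4 defines time to resolution as stop date minus start date plus 1 and refers to 6.3. "The presentation will include the continuous variable and also by categorizing the number of days until the resolution of infection". The last category is 14 days or more; there is no category for ongoing. Kaplan-Meier plots are planned, without a censoring rule.
- SAP 8.2.2 adds a day-based rate: "The annual rate of days with infections per subject will be the total number of days with infections of the subject divided by the total"; the divisor is the subject's observation time in years. SAP 8.2.3 does the same for nonserious infections. By SAP 8.1.1 the observation period runs from first infusion to last visit.

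**The concern.** Whether an infection has a stop date depends on how long it lasts: the longer the episode, the more likely it is to be cut off by the closing visit or by withdrawal. A summary restricted to episodes with a stop date therefore selects on the outcome it describes. Time to resolution is a listed secondary efficacy endpoint (SAP 4.2), and both it and the infection-day rates would look more favourable than the data warrant.

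The plan also treats two records of one illness differently. An antibiotic course with no stop year is run to study termination and enters the antibiotic-day rates of SAP 8.2.5. The infection it treats, if still open, has no duration and no day-count rule.

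**Working it through.** The plan states no figure on this point, so there is none to reproduce. The check first follows the rules through, then sizes the effect under assumptions.

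**Following one open infection through the plan**

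1. Open at the last visit, not serious, severe or related: follow-up ends and there is no end date (Protocol 9.3.4, Appendix 1).
2. No imputation applies (SAP 6.3).
3. Stop minus start plus 1 cannot be evaluated, so the episode has no value in the mean, median or category table (SAP 8.2.4).
4. Days with infection: no rule (SAP 8.2.2, 8.2.3). If the days need a stop date, the numerator loses them; the denominator is unchanged.
5. Number of infections: unaffected, because the episode is counted without a stop date.

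**Illustration for one subject.** Follow-up is 379 days (3-week schedule, flowchart). If the open days are not counted, the subject's rate is short by open days / 379 × 365:

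- 7 open days: 7/379 × 365 = 6.7 days per year; over 70 subjects, 6.7/70 = about 0.1.
- 60 open days, an extreme case: 60/379 × 365 = 57.8 days per year; over 70 subjects, 57.8/70 = 0.83.

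**Trial-level size.** From the documents: about 70 subjects (SAP 3.5) and follow-up of 379 or 393 days; the midpoint, 386, is used. Assumed, because the documents do not give them: 2 to 4 infections per subject-year, mean duration 7 to 21 days, lognormal with coefficient of variation (CV) 0.7 to 1.5, and 0 to 20 of 70 subjects leaving early.

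With no early leavers, the share of infections open at exit is about mean duration / follow-up: 7/386 = 1.8%, 21/386 = 5.4%. The expected number is 70 × rate/365 × mean duration: 70 × 2/365 × 7 = 2.7, up to 70 × 4/365 × 21 = 16.1. Simulation over the assumed grid agrees. Three of its scenarios:

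| Rate per year; mean days; CV; early leavers | Open at exit | Mean days, all → resolved only | Lasting ≥14 days, all → resolved only | In-study infection days lost if not counted | Median days, all / Kaplan-Meier |
|---|---|---|---|---|---|
| 4; 7; 0.7; 0 | 1.8% | 7.00 → 6.94 | 7.9% → 7.6% | 1.4% | 5.74 / 5.74 |
| 4; 14; 1.5; 20 | 4.2% | 14.00 → 12.75 | 29.4% → 27.7% | 6.7% | 7.79 / 7.79 |
| 2; 21; 1.5; 20 | 6.2% | 20.96 → 18.20 | 43.3% → 40.8% | 9.9% | 11.67 / 11.67 |

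The falls in mean are (7.00 − 6.94)/7.00 = 0.9%, (14.00 − 12.75)/14.00 = 8.9% and (20.96 − 18.20)/20.96 = 13.2%. Over the whole grid, 1.8% to 6.3% of infections are open at exit, and the share lasting 14 days or more falls by 0.3 to 2.5 percentage points. Kaplan-Meier with censoring at the last visit recovers the median and the 14-day share in every scenario. Of the open episodes, 14% to 27% are shorter than the median infection.

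**The case against.** The strongest reply is that SAP 6.3 is right. Inventing a stop date for an infection that has not resolved would create a false resolution, and a Kaplan-Meier analysis needs such episodes left open. That stands: the fault lies in what 8.2.2 to 8.2.4 do with an open episode, not in the refusal to impute.

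Kaplan-Meier plots are planned, so open episodes need not vanish from the endpoint. That stands too, but a plot without a stated censoring date does not correct the tabulated mean, median and categories.

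Serious, severe or related infections are followed past the last visit, and Appendix 1 asks sites to seek an end date. This narrows the problem to other infections and to failed follow-up. It also exposes a gap in the other direction: a stop date after the last visit could add infection days outside the denominator.

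The effect is confined to descriptive results. The infection-day rate is not itself among the secondary endpoints listed in SAP 4.2, and AE listings will still show open episodes.

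A reader might go further and infer that the plan scores an open infection as zero days. The documents do not say so: 8.2.2 and 8.2.3 are silent, the 6.3 default is missing rather than zero, and the days up to the last visit are observed and could be counted. Nor do they support saying that the longest infections are removed. The omitted ones are longer on average, but an infection that starts just before the closing visit is open as well.

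**Conclusion.** The point holds for the tabulated time-to-resolution summaries: the stated rules restrict them to resolved episodes, and the bias is toward shorter durations. For days with infection the defect is an absent rule, with loss of days the likely result. Under the assumed ranges the fall in mean duration is about 1% to 13%; if open days are not counted, 1.4% to 9.9% of in-study infection days are lost. These sizes rest on rates and durations that the documents do not give and should not be read as estimates for this trial. The good Kaplan-Meier recovery further requires that leaving the study is unrelated to how the infection would have continued; withdrawal because of an infection would weaken it.

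Nothing here touches the primary endpoint, infection counts or infection rates. It is still worth correcting, because a listed secondary endpoint would be summarised with a known direction of bias and the remedy needs no new data.

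**What to change.** Leave the ongoing-AE restriction in SAP 6.3 as it is, and add the following.

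1. **SAP 8.2.2 and 8.2.3:** for an infection ongoing at the last visit, count days from onset through the last visit, which is where the denominator ends. Cut off at the same date any infection that resolves later.
2. **SAP 8.2.4:** use the actual resolution date when later follow-up supplies one; otherwise censor at the last visit or last follow-up contact. Censoring everything at the last visit would discard known later resolutions.
3. **SAP 8.2.4 tables:** show the number of ongoing infections as its own row in the category table. Report the Kaplan-Meier median next to the existing summary, and label the latter as resolved episodes only.

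The cost is a few sentences and minor programming. Infection-day and duration figures may come out slightly less favourable.

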#### Missing start time of AE

In case, AE can be assumed as infusional AE (started on the date of infusion or within 72 hours after last infusion), time will be imputed as 00:00. If date of AE start = Date of infusion start, date/time of AE start will be assumed as the date/time of the infusion start.

In case an Investigator comment is available for the assumed infusional AE, imputation will take this into account:

- AE started before treatment: time will be imputed as 00:00
- AE started during treatment: time will be imputed as start time of infusion
- AE started after treatment: time will be imputed as one minute after end of infusion

#### Missing stop time of AE:

In case, AE can be assumed as infusional AE (started on the date of infusion or within 72 hours after last infusion, missing stop time will be imputed with end of day: 23:59

#### Incomplete PID diagnosis date will be imputed

Missing start day with '15'.

Missing start day and month with the '15' of July.

#### Incomplete severity / seriousness and/or relationship:

In situations where an AE has a missing severity / seriousness and/or relationship, a worstcase scenario will be applied. That is, missing severities will be imputed as 'severe', missing seriousness will be imputed as serious, while missing relationships will be imputed as 'related'. 'Related' relationship will be only be imputed after start of first drug administration. During screening phase the relationship will be not related.

#### Missing body weight assessment:

In case body weight assessment is missing at any visit the last available body weight assessment of the subject will be used for the calculation of the actual dose.

#### 6.4. VISIT WINDOWS

A tolerance for the visit day of  $\pm 2$  days will be allowed for the treatment visits and closing (follow-up) visit; however, all visits will be summarized according to the nominal visit. Different rules may apply for the analysis of pharmacokinetics.

#### 6.5. POOLING OF CENTERS

Data from all centers will be pooled together. Serum concentrations estimated in the course of the study for dosing decisions (by local laboratories) may be separated from the serum concentrations estimated by central laboratories for formal the PK analyses.

#### 6.6. SUBGROUPS

There are 4 defined subgroups: age, gender, race and region (US vs. Europe vs. Asia).

Two age categories for the subgroup analyses are defined:

- Age category according to FDA young children (2 to <6 years), children (6 to <12 years) adolescents (12 to <17 years) adults (17 to <76 years) geriatric (>=65 years)
- Age category according to EMA young children (2 to <6 years), children (6 to <12 years) adolescents (12 to <18 years) adults (18 to <76 years) geriatric (>=65 years)

The pediatric population (young children, children and adolescents) will be presented as a subtotal.

Age is the age recorded at screening (initial visit) by the investigator. The same age is used per subject during the entire study (i.e., if a subject's age changes from 17 to 18 years during the study, the subject remains in the age category of 12 through 17 years during the entire study).

The subgroup analysis will be performed within the treatment schedule (3-week and 4-week) and overall, if not stated otherwise, for:

- All demographics, other baseline characteristics and medication (section 7)
- All efficacy endpoints (primary and secondary) (section 8)
- All safety parameters (section 11)
- All PK parameters (section 9)

7.

DEMOGRAPHIC, OTHER BASELINE CHARACTERISTICS AND MEDICATION

The summary statistics will be based on the FAS and will be done by treatment schedule (3- or 4- week) and overall, if not stated otherwise.

In addition, all Demographic, other baseline characteristics and medication will be summarized descriptively stratified by age categories, gender, race and region as defined in Section 6.6. Age classes will be presented separately by FDA and by EMA criteria. The pediatric population (young children, children and adolescents) will be presented as a subtotal.

